**Table 3: Adverse Event Grading**

Severity	Definition
Grade 1	Mild; asymptomatic or mild symptoms, clinical or diagnostic observations only; intervention not indicated.
Grade 2	Moderate; minimal, local or noninvasive intervention indicated; limiting age-appropriate instrumental ADL.
Grade 3	Severe or medically significant but not immediately life-threatening; hospitalization or prolongation of hospitalization indicated; disabling; limiting self care ADL.
Grade 4	Life-threatening consequences; urgent intervention indicated.
Grade 5	Death related to AE.

**Clarification between Serious and Severe:** The term “severe” is often used to describe the intensity (severity) of a specific event (as in mild, moderate, or severe myocardial infarction); the event itself, however, may be of relatively minor medical significance (such as severe headache). This is not the same as “serious,” which is based on the outcome or action criteria usually associated with events that pose a threat to life or functioning. Seriousness (not severity) and causality serve as a guide for defining regulatory reporting obligations.

#### 7.13.1.4. Data Monitoring Committee

A DMC will be established to review safety data from this study, thereby better ensuring the safety of study participants. Consistent with US Food and Drug Administration (FDA) recommendations (FDA Guidance for Industry, Establishment and Operation of Clinical Trial Data Monitoring Committees, 2006), the DMC will be constituted of independent clinicians expert in the field of MF and clinical research. A formal charter will be established for the conduct of the DMC.

The committee is planned to review unblinded safety data at periodic intervals. The DMC may ask to schedule ad-hoc meetings as needed. No interim efficacy data are planned to be reviewed by the DMC. Details of safety review are provided in the DMC Charter.

#### 7.13.1.5. Relatedness of Adverse Events and Serious Adverse Events

Relationship of an AE or SAE to investigational product is to be determined by the Investigator based on the definitions in [Table 4](#).

**Table 4: Adverse Event Relatedness**

Relationship to Product(s)	Definition
Not Related	Unrelated to investigational product.
Possibly Related	A clinical event or laboratory abnormality with a reasonable time sequence to administration of investigational product, but which could also be explained by concurrent disease or other drugs or chemicals.
Probably Related	A clinical event or laboratory abnormality with a reasonable time sequence to administration of investigational product, unlikely to be attributable to concurrent disease or other drugs and chemicals and which follows a clinically reasonable response on de-challenge. The association of the clinical event or laboratory abnormality must also have some biologic plausibility, at least on theoretical grounds.

### **7.13.2. Procedures for Recording and Reporting Adverse Events**

#### **7.13.2.1. Adverse Event Monitoring and Period of Observation**

Adverse events (AEs) will be monitored continuously throughout the study.

For the purposes of this study, the period of observation extends from the time at which the subject or the subject's legally authorized representative gives informed consent until the subject's final evaluation of the study. If the Investigator considers it necessary to report an AE in a study subject after the end of the safety observation period, he or she should contact the Sponsor to determine how the AE should be documented and reported.

#### **7.13.2.1.1. Reporting of Adverse Events of Special Interest**

The Investigator must report suspected Infusion Related Reaction, regardless of severity, on an Adverse Event of Special Interest (AESI) form. This form must be completed and submitted, either by e-mail or fax, immediately but no later than 24 hours of the Investigator's learning of the event to Pivotal's Safety Unit:

- e-mail: [[contact]](mailto:[contact])

- Fax (US SAEs): [contact]
- Fax (non-US SAEs): [contact]

#### **7.13.2.2. Reporting Serious Adverse Events**

The Investigator must report all SAEs to the Safety Unit of Pivotal S.L. within 24 hours of discovery either by e-mail or fax to:

- e-mail: [[contact]](mailto:[contact])
- Fax (US SAEs): [contact]
- Fax (non-US SAEs): [contact]

A completed SAE report is to be sent to Pivotal's Safety Unit within 24 hours of discovering the event. The initial report should include at least the following information:

- Subject's Study Number;
- Description and date of the event;
- Criterion for serious; and
- Preliminary assignment of causality to study drug.

The Safety unit will contact the Investigator either by email or telephone for follow-up information regarding the SAE, as appropriate.

The Investigator must promptly report all required information to the Institutional Review Board (IRB)/Independent Ethics Committee (IEC)/Research Ethics Boards (REB). It is the responsibility of the Sponsor to ensure that each Investigator receives a copy of any CIOMS I/MedWatch report that has been submitted to the appropriate regulatory agencies notifying them of an unexpected related SAE. The Investigator or Sponsor must ensure that the IRB/IEC/REB receives a copy of the report and that a copy is also filed within their study files.

#### **7.13.3 Reporting Pregnancies**

Pregnancy itself is not considered an AE. If a subject becomes pregnant or the partner of a subject participating in the study becomes pregnant during the study or within 3 months of discontinuing any study drug, the Investigator should report the pregnancy on a separate pregnancy report form provided to the sites. Only pregnancies occurring from the time of first study treatment dose administered to the subject will be reported and documented. The study treatment will be immediately discontinued for any female subject who becomes pregnant during study participation, if study treatment is ongoing at that time. The subject/partner should be followed by the Investigator until completion of the pregnancy. If the pregnancy ends for any reason before the anticipated date, the Investigator should notify the Sponsor. At the completion of the pregnancy, the Investigator will document the outcome of the pregnancy. This pregnancy report form must be completed and submitted, either by e-mail or fax, immediately but no later than 24 hours of the Investigator's learning of the event to Pivotal's Safety Unit:

- e-mail: [[contact]](mailto:[contact])

- Fax (US SAEs): [name]
- Fax (non-US SAEs): [contact]

Any pregnancy complication, spontaneous or elective abortion, still birth, neonatal death, or congenital anomaly will be recorded as an AE or SAE, and reported, as applicable.

#### **7.13.4. Medication Error**

A medication error is defined as a mistake made in prescribing, dispensing, administration and/or use of the investigational medicinal product. All medication errors must be recorded in the eCRF.

### **7.14. Removal of Subjects from the Trial or Investigational Product**

A subject's participation in the study may be discontinued at any time at the discretion of the Investigator. The following may be justifiable reasons for the Investigator to remove a subject from the study:

- Non-compliance, including failure to appear at one or more study visits;
- The subject withdraws consent;
- The subject was erroneously included in the study;
- The subject develops an exclusion criterion;
- The subject suffers an intolerable adverse event;
- The subject becomes pregnant;
- The study is terminated by the Sponsor.

The subject is free to withdraw consent and discontinue participation in the study at any time without prejudice to further treatment. If a subject discontinues participation in the study, or the subject is discontinued by the Investigator, the Investigator will notify the Sponsor and, when possible, will perform the procedures indicated for the final visit. Follow-up information will be obtained during the final telephone contact, if possible, for subjects who discontinue their participation in or are withdrawn from the study.

Any adverse events (AEs) experienced up to the point of discontinuation must be documented on the AE eCRF. If AE's are present when the subject withdraws from the study, the subject will be re-evaluated within 30 days of withdrawal. All ongoing SAEs at the time of withdrawal will be followed until resolution.

Subjects withdrawn from the study will be replaced at the discretion of the medical monitor and the Investigator. A replacement subject will be randomized to treatment with single agent PRM-151 at doses of 0.3, 3, or 10 mg/kg IV.

### **7.15. Other Study Procedures**

Not applicable

### **7.16. Appropriateness of Measurements**

Subjects will be assessed for safety at all visits based on history, physical examination, and laboratory values. Subjects will be assessed for efficacy every four weeks by hematologic parameters (Hgb, WBC with differential, ANC, and platelet count), measurement of splenomegaly, and symptom assessment, and at Weeks 12, 24, and 36 by bone marrow biopsy to assess change in fibrosis. Global assessment of fibrosis will be assessed at Baseline, Weeks 12, 24, and 36 by FDG or FLT PET-CT.

## 8.0 STAGE 2 STUDY ACTIVITIES

The Schedules of Events can be found in [APPENDIX A](#). Quality of Life assessments (MPN-SAF and EORTC QLQ-C30) should be done as early in the visit as possible and prior to phlebotomy, bone marrow biopsy or any other procedure that may affect subject responses. In the event the central lab cannot be used to get a reliable result for a laboratory test, local laboratory tests may be used after this has been agreed upon by the Medical Monitor.

### 8.1. Screening Visit ( $\leq$ 28 Days Prior to First Dose)

- Provide written informed consent
- Recording of demographics and medical history
- Assessment of inclusion/exclusion criteria
- MPN-SAF
- EORTC QLQ-C30
- IWG-MRT DIPPS (risk assessment)
- Bone marrow biopsy (< 4 weeks prior to first dose)
- Abbreviated physical examination with spleen measurement (as defined in [Table 1](#)).
- Recording of prior and concomitant medications
- Assessment of Adverse Events
- Vital signs
- Height and weight
- ECOG Performance Status
- Serum pregnancy test for women of child-bearing potential (central lab (< 4 weeks prior to first dose))
- Complete blood count (CBC) (central lab)
- Chemistry evaluations (central lab)
- Coagulation parameters (central lab)
- 12 lead Electrocardiogram (ECG)
- Review of transfusions
- Review of excluded medications
- Access IRS to register subject

## **8.2. Cycle 1, Day 1 (+/- 1 day)**

- FDG or FLT PET-CT (where feasible) or CT or MRI (within 2 weeks prior to C1D1)
- Update medical history
- Re-assess inclusion/exclusion criteria
- MPN-SAF
- EORTC QLQ-C30
- IWG-MRT DIPSS (risk assessment)
- Abbreviated physical exam with spleen measurement
- Recording of concomitant medications
- Monitoring of adverse events
- Vital signs (before, immediately after study drug infusion and 1 hour post infusion)
- Weight
- ECOG Performance Status
- Urine pregnancy test for women of child-bearing potential (local lab)
- Complete blood count (CBC) (central lab)
- Chemistry evaluations (central lab)
- Coagulation parameters (central lab)
- Blood sample for Infusion Related Reaction Cytokines and anti-pentraxin 2 antibodies (pre-dose)
- Blood samples for genetic analysis
- Review of transfusions
- Review of excluded medications
- Blood sample for pentraxin-2 levels (pre-dose)
- Blood sample for anti-pentraxin 2 antibodies (pre-dose)
- Unblinded Pharmacist (or designee) to access IRS to randomize subject to dosing cohort
- PRM-151 administration

## **8.3. Cycle 1, Days 3 and 5 (+/- 1 day)**

- Recording of concomitant medications
- Monitoring of adverse events
- Vital signs
- ECOG Performance Status
- Unblinded Pharmacist (or designee) to access IRS to confirm dosing
- PRM-151 administration

#### **8.4. Cycles 2 through 9, Day 1 (+/- 3 days)**

- MPN-SAF
- EORTC QLQ-C30
- IWG-MRT Response Assessment (PMF, post-EV MF and post PV MF patients)
- Bone marrow biopsy (Cycle 4 and Cycle 7, Day 1 +/- 3 days)
- FDG or FLT PET-CT (where feasible) or CT or MRI (Cycle 4 and Cycle 7, Day 1 +/- 3 days)
- Abbreviated physical exam with spleen measurements
- Response Assessment
- Recording of concomitant medications
- Monitoring of adverse events
- Vital signs
- Weight
- ECOG Performance Status
- Urine pregnancy test for women of child-bearing potential (local lab)
- Complete blood count (CBC) (central lab)
- Chemistry evaluations (central lab)
- Coagulation parameters (central lab)
- Review of transfusions
- Review of excluded medications
- Blood sample for pentraxin -2 levels (pre-dose)
- Blood sample for anti pentraxin 2 antibodies (pre-dose)
- Unblinded Pharmacist (or designee) to access IRS to confirm dosing
- PRM-151 administration

#### **8.5 Cycle 9, Day 29 (Week 36) (+/- 3 days)**

- MPN-SAF
- EORTC QLQ-C30
- IWG-MRT DIPSS (risk assessment)
- IWG-MRT Response Assessment (PMF, post-EV MF and post PV MF patients)
- PET-CT or CT or MRI (+/- 3 days)
- Bone marrow biopsy (+/- 3 days)
- Abbreviated physical exam with spleen measurements
- Recording of concomitant medications
- Monitoring of adverse events
- Vital signs
- ECOG Performance Status
- Complete blood count (CBC) (central lab)

- Chemistry evaluations (central lab)
- Coagulation parameters (central lab)
- Review of transfusions
- Review of excluded medications
- Blood sample for pentraxin-2 levels (pre-dose if continuing treatment in extension)
- Blood sample for anti-pentraxin 2 antibody (pre-dose)
- Blood samples for genetic analysis

**8.6. End of Study Visit (approximately 28 days [+/- 3 days] after Cycle 9 Day 29 or withdrawal from study)**

- MPN-SAF
- EORTC QLQ-C30
- Abbreviated physical exam and spleen measurement
- Recording of concomitant medications
- Monitoring of adverse events
- Vital signs
- ECOG Performance Status
- Complete blood count (CBC) (central lab)
- Chemistry evaluations (central lab)
- Review of transfusions
- Review of excluded medications

## **9. QUALITY ASSURANCE AND CONTROL**

Training will occur at the site initiation visit; instruction manuals will be provided to aid consistency in data collection and reporting across sites.

Clinical sites will be monitored by the Sponsor or its designee to ensure the accuracy of data against source documents.

The required data will be captured in a validated clinical data management system that is compliant with the FDA 21 Code of Federal Regulations (CFR) Part 11 Guidance. The clinical trial database will include an audit trail to document any evidence of data processing or activity on each data field by each user. Users will be trained and given restricted access, based on their role(s) in the study, through a password-protected environment.

Data entered in the system will be reviewed manually for validity and completeness against the source documents by a clinical monitor from the Sponsor or its designee. If necessary, the study site will be contacted for corrections or clarifications; all missing data will be accounted for.

## 10. STAGE 2 PLANNED STATISTICAL METHODS

### 10.1 Determination of Sample Size

The chosen sample size of 72 subjects (i.e. 24 subjects per dose arm) is deemed sufficient to provide adequate precision to the estimation of the response rate in each treatment arm. The trial will enroll 84 subjects to allow for a discontinuation rate of 15%.

On the basis of the available data, it is assumed that the response rate on the primary endpoint will be 5% in the 0.3 mg/kg arm, 46% in the 10 mg/kg arm and at least 46% in the 3 mg/kg arm. A sample size of 24 subjects will ensure an absolute precision of +/- 8% to the evaluation of the response rate in the 0.3 mg/kg arm (assuming the response rate is 5%) and an absolute precision of +/- 20% of the response rate in the 3 mg/kg and 10 mg/kg arms (assuming the response rate is 46%).

In addition, with 24 subjects in each arm, the probability to demonstrate that the observed response rate in the 3 mg/kg and 10 mg/kg arms is larger than 10% by comparing the lower limit of the exact 97.5% two-sided confidence interval of the observed rate to 10% is larger than 0.999 (assuming the response rate is 46%)

In addition, it is planned to perform pairwise comparisons between dose arms as part of the secondary efficacy analysis. A sample size of 24 subjects per arm will ensure a power of 82% to detect a difference of 39% between two treatment arms (assuming the best response rate is 46%) with a two-sided type one error of 0.025. Consequently if the assumption of response rates of 5% in the 0.3 mg/kg arm and 46% in the 3 and 10 mg/kg arm is true, the study will be sufficiently powered (power = 82%) to demonstrate a significant superiority of any of the higher doses over the smallest dose, using an adjusted two-sided 0.025 type-one error rate.

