**Primary analysis of efficacy**

The primary efficacy analysis will consist in computing the bone marrow response rate (percent of subjects with a reduction in bone marrow fibrosis score by at least one grade) and its 97.5% two-sided confidence interval within each treatment arm. This analysis will be conducted on the FAS analysis set.

Inferential interpretation: for the 3 mg/kg and 10 mg/kg arms, the lower limit of the 97.5% two-sided confidence interval will be compared to 10%, a threshold assumed to define the minimal clinically relevant effect. If the lower limit of the confidence interval is above 10%, the corresponding dose will be claimed to have demonstrated clinically relevant efficacy.

The confidence intervals computation will use a method consistent with the stratified design.

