### **10.3.3. Inferential statistics**

The primary efficacy analysis is both descriptive and inferential. The exact confidence interval for the response rate in each arm will be computed and its lower bound will be compared to 10%.

In addition, one secondary objective of the study is to determine if there is a difference in efficacy between the three doses of PRM-151 used in the study. These comparisons will be done only if at least one dose arm is demonstrated to have a response rate superior to 10% in the primary analysis. The comparison between the 3 mg/kg arm and 10 mg/kg arm is not expected to be sufficiently powered to detect any statistically significant difference. The two main comparisons (3 mg/kg arm versus 0.3 mg/kg arm and 10 mg/kg arm versus 0.3 mg/kg) will use an adjusted type-one error rate of 0.025 to control the overall type-one error rate. The 3 mg/kg versus 10 mg/kg comparison will only be provided with an exploratory purpose and will be done without correction of the type-one error.

For all the other secondary efficacy analyses involving formal statistical comparisons, no adjustment of the type-one error rate will be conducted. As a consequence, the results of these tests will have to be interpreted bearing in mind the issue of multiplicity and the increased risk of erroneously obtaining statistically significant results.

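### Protocol 10.1 promises +/-8% and +/-20% precision from an unnamed 95% normal approximation; the planned exact intervals are wider, materially so at a 5% response rate

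*Protocol*

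**What the plan says.** Protocol 10.1 (Determination of Sample Size) gives precision as the first reason for 24 subjects per arm. It assumes that "the response rate on the primary endpoint will be 5% in the 0.3 mg/kg arm, 46% in the 10 mg/kg arm", with at least 46% at 3 mg/kg. From this it states: "A sample size of 24 subjects will ensure an absolute precision of +/- 8% to the evaluation of the response rate" in the 0.3 mg/kg arm, and "an absolute precision of +/- 20% of the response rate in the 3 mg/kg and 10 mg/kg arms". No confidence level or method is attached to either figure. The synopsis, which SAP Appendix 3 reproduces, gives no precision figures and refers to the body of the protocol, so 10.1 is the only place where they appear.

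The interval planned for the analysis is described elsewhere:

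- **Protocol 10.1, next paragraph:** the 10% threshold is judged with an exact 97.5% two-sided interval.
- **Protocol 10.3.3:** "The exact confidence interval for the response rate in each arm will be computed", and its lower bound is set against 10%.
- **Synopsis, primary analysis:** the response rate and "its 97.5% two-sided confidence interval within each treatment arm".
- **Protocol 10.6.1.1:** two intervals per arm, 95% unadjusted and 97.5% adjusted. The 97.5% lower limit is compared with 10% in the 3 and 10 mg/kg arms only. The same section, like the synopsis, also asks for a method that fits the stratified design.
- **SAP 4.4.1:** a 95% interval is presented per group, and the 97.5% lower limit is applied to the 10% threshold. No interval method is named.

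**The concern.** A precision statement in a sample-size section should describe the interval that will be reported. This one carries no label, and its values do not match an exact interval at either planned level. The primary objective is to determine the effect size of each dose, so interval width is central to what the trial can deliver.

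The mismatch matters most in the 0.3 mg/kg arm. About 1.2 responders are expected there (24 x 0.05), and the normal approximation puts its lower limit below zero (5% - 8.7%). A reader who takes +/-8% at face value expects an upper limit near 13% (5% + 8%). One responder in 24 in fact gives an exact upper limit above 20% at either level. This arm is also the reference for both superiority comparisons.

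**Working it through.** **Inputs.** n = 24 per arm; assumed rates 5% and 46% (Protocol 10.1); exact interval (10.1, 10.3.3); levels 95% and 97.5% (10.6.1.1). The documents name no particular exact method; Clopper-Pearson, without stratification, is assumed.

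**1. Reproducing the stated figures.** The normal-approximation half-width is z x sqrt(p(1-p)/n), with z = 1.96 for 95%.

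- Whole counts: p = 1/24 gives 1.96 x sqrt((1/24)(23/24)/24) = 7.99%; p = 11/24 gives 19.93%.
- Exact rates: p = 0.05 gives 1.96 x sqrt(0.05 x 0.95/24) = 8.72%; p = 0.46 gives 1.96 x sqrt(0.46 x 0.54/24) = 19.94%.

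Both stated values are therefore recovered at 1/24 and 11/24. Neither the 97.5% normal interval (z = 2.2414: 9.97% and 22.80%) nor the 95% Wilson interval (10.2% and 18.5%) gives the pair.

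**2. The planned exact interval.** For x responders, the lower limit is the alpha/2 quantile of Beta(x, n-x+1) and the upper limit is the 1-alpha/2 quantile of Beta(x+1, n-x). The expected half-width is the average of (upper - lower)/2 over x distributed as Binomial(24, p).

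| | Stated in 10.1 | Exact 95% | Exact 97.5% |
|---|---|---|---|
| Rate 5%, expected | 8 | 10.6 | 12.0 |
| 1/24 observed | | 10.5 | 11.9 |
| Rate 46%, expected | 20 | 20.4 | 22.8 |
| 11/24 observed | | 20.8 | 23.2 |

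(Half-widths in percentage points.)

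**3. Whether +/-8% can be reached at all.** The narrowest exact interval comes at zero responders. At 97.5% it runs from 0 to 16.69%, a half-width of 8.3 points, so no possible result with n = 24 achieves 8. At 95%, 0/24 gives 0 to 14.25% (7.1 points) but 1/24 already gives 10.5. With a true rate of 5%, the chance of 0/24 is 0.95^24 = 29%.

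**4. Asymmetry at 5%.** For 1/24 (4.2%) the exact 97.5% interval is 0.05% to 23.8%, which is 4.1 points below the estimate and 19.6 above. The exact 95% interval is 0.1% to 21.1%. A single +/- figure hides this.

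**5. If all enrolled subjects are analysed.** With 84/3 = 28 per arm, the expected exact half-widths are 9.7 (95%) and 11.0 (97.5%) points at 5%, and 19.0 and 21.2 points at 46%.

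**The case against.** Several counter-arguments have force.

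- **The figures are not a calculation slip.** A reader might infer that 10.1 miscomputed, because exactly 5% gives 8.7%, and that more subjects would be needed to reach 8%. The documents do not support that: at the nearest whole counts the 95% normal formula returns both stated values. The fault is the choice of an unlabelled approximation.
- **97.5% is not the only level.** A reader of the synopsis alone might judge both figures only against the 97.5% interval. Protocol 10.6.1.1 and SAP 4.4.1 also plan a 95% interval, a reasonable level for describing estimation. On that basis +/-20% is close to right.
- **No threshold claim rests on the 0.3 mg/kg interval.** Only the two higher doses are tested against 10%, and the dose comparisons use other methods. This limits the consequence. It does not make the stated precision for that arm correct.
- **The method is not fully fixed.** Exact and stratification-consistent both appear, so unstratified exact figures could themselves prove not to describe the final interval. This stands and belongs in the fix.
- **More than 24 may be analysed.** The SAP's primary population (4.1.1) is all randomized and treated subjects, with those lacking a readable biopsy counted as non-responders, so n could approach 28. That brings the 46% figure within +/-20% at 95% and within about a point of it at 97.5%. At 5% the half-width stays near 10 to 11 points.

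**Conclusion.** The point holds in a limited form. The precision in 10.1 was calculated with a normal approximation that the plan does not otherwise call for, and it is not labelled as such. At 5% the promised +/-8% is about 2.6 points short of the expected exact half-width at 95% (10.6) and 4 points short at 97.5% (12.0). Analysing 28 per arm does not rescue it. At 46%, +/-20% nearly holds at 95% (20.4) and is about 3 points too favourable at 97.5% (22.8).

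A reader might go further and conclude that 24 per arm is inadequate. That does not follow: the protocol sets no half-width as a requirement, and the threshold rule and the dose comparisons do not use these figures. The results above assume Clopper-Pearson limits, no stratification, n = 24 and the protocol's own response rates.

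**What to change.** In Protocol 10.1, name the interval and restate the expected precision for n = 24 (exact, unstratified):

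- at a 5% rate, about +/-11 points (95%) and +/-12 points (97.5%);
- at a 46% rate, about +/-20 points (95%) and +/-23 points (97.5%).

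Add that the interval at 5% is strongly asymmetric, with 1/24 as the example (0.05% to 23.8% at 97.5%). Reconcile the exact interval of 10.3.3 with the stratification-consistent method of the synopsis and 10.6.1.1, and name the chosen method in SAP 4.4.1 as well. If a stratified method is chosen, recompute the four figures for it.

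The cost is one reworded paragraph plus one settled method statement. Sample size, endpoint and decision rule are unchanged; the stated precision becomes less favourable.

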## 10.6. Planned Statistical Analyses and Methods

### 10.6.1 Efficacy Analyses

#### 10.6.1.1. Primary analysis of efficacy

The primary efficacy analysis will consist in computing the bone marrow response rate (percent of subjects with a reduction in bone marrow fibrosis score by at least one grade, see Section 3.1) and its 95% (unadjusted) and 97.5% (adjusted) two-sided confidence intervals within each treatment arm. This analysis will be conducted on the FAS analysis set.

Inferential interpretation: for the 3 mg/kg and 10 mg/kg arms, the lower limit of the 97.5% two-sided confidence interval will be compared to 10%, a threshold assumed to define the minimal clinically relevant effect. If the lower limit of the confidence interval is above 10%, the corresponding dose will be claimed to have demonstrated clinically relevant efficacy.

The confidence intervals computation will use a method consistent with the stratified design.

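### Protocol 10.1 puts the chance that a dose clears the 10% threshold above 0.999; under the rule it names, with 24 subjects and a 46% response rate, the chance is 0.97 per dose.

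*Protocol*

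**What the plan says.** Protocol 10.1 sets "The chosen sample size of 72 subjects (i.e. 24 subjects per dose arm") and assumes response rates of "5% in the 0.3 mg/kg arm, 46% in the 10 mg/kg arm and at least 46% in the 3 mg/kg arm". It first justifies 24 per arm by precision. It then gives a probability of success for the primary claim: at a true rate of 46%, the probability found by comparing the lower limit of the "exact 97.5% two-sided confidence interval of the observed rate to 10% is larger than 0.999".

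Two other sections say how the rule is applied. Protocol 10.3.3: "The exact confidence interval for the response rate in each arm will be computed and its lower bound will be compared to 10" percent. Protocol 10.6.1.1 makes the claim dose by dose for the 3 and 10 mg/kg arms: if the lower limit is above 10%, "the corresponding dose will be claimed to have demonstrated clinically relevant efficacy". SAP 4.4.1 keeps the same 97.5% rule for each of these two groups. It gives no new probability: SAP 2.5 refers sample size to the synopsis, and the synopsis refers back to the body of the protocol.

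**The concern.** The sentence fixes the sample size, the true rate, the interval method and level, and the threshold, so the probability is fully determined and can be checked. A value above 0.999 looks too high for 24 subjects and an exact interval.

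It is the only chance of success that the plan states for the primary efficacy claim. A reader would conclude that, if the 46% assumption is right, a dose practically cannot miss. If a dose did miss, that reader would treat the result as near-proof that the true rate is below 46%, when a miss at 46% has roughly a 3% chance. Because the SAP does not restate the figure, it could pass unchanged into the study report.

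**Working it through.** **Inputs.** From protocol 10.1: n = 24 per arm, true rate 0.46, exact two-sided 97.5% interval (0.0125 in the lower tail), threshold 0.10. From protocol 10.3.3 and 10.6.1.1: the rule is applied in each arm, and the claim is made per dose.

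**Step 1: cut-off.** The exact (Clopper-Pearson) lower limit for x responders is the 0.0125 quantile of a Beta(x, n − x + 1) distribution.

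| Responders of 24 | Lower limit | Above 10%? |
|---|---|---|
| 4 | 3.8% | no |
| 5 | 6.0% | no |
| 6 | 8.4% | no |
| 7 | 11.0% | yes |
| 8 | 13.8% | yes |

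A dose therefore needs at least 7 responders. At a true rate of 10%, the chance of 7 or more is 0.0075, within the 0.0125 allowed.

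**Step 2: probability at 46%.** With X binomial (24, 0.46), P(X ≤ 6) = 0.0293, so P(X ≥ 7) = 1 − 0.0293 = **0.971**. The stated value is above 0.999.

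**Step 3: both doses, or either dose** (arms independent, 46% in each).
- Both clear: 0.9707² = 0.942, so at least one misses with probability 1 − 0.942 = 0.058.
- At least one clears: 1 − 0.0293² = 0.9991.

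**Step 4: could another per-dose reading give the stated figure?**

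| Reading (true rate 46%) | Cut-off | Probability per dose |
|---|---|---|
| Exact 97.5%, n = 24 (as written) | 7 | 0.971 |
| Exact 95%, n = 24 | 7 | 0.971 |
| Jeffreys or mid-p 97.5%, n = 24 | 7 | 0.971 |
| Wilson 97.5%, n = 24 | 6 | 0.990 |
| Wald 97.5%, n = 24 | 8 | 0.928 |
| Exact 97.5%, n = 28 (all 84 enrolled) | 8 | 0.981 |

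None reaches 0.999. To exceed it at n = 24, the cut-off would have to be 4 responders or fewer (P(X ≥ 4) = 0.9994; P(X ≥ 5) = 0.9973), and 4/24 has a lower limit of only 3.8%. Under the exact 97.5% rule, 0.999 per dose needs either a true rate of about 58% with 24 subjects, or 42 subjects per arm at 46% (cut-off 10, probability 0.99914; 41 subjects give 0.99873).

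A normal approximation that uses the null variance, 0.10 × 0.90/24, under both hypotheses gives 0.9999 per dose. It is not an exact calculation and assigns the wrong variance to a 46% rate. With the variance of a 46% rate under the alternative, the approximation gives 0.986.

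**Neighbouring figures in 10.1.** The 82% power reproduces as a single pairwise comparison. For 46% against 7%, with a two-sided level of 0.025 (z = 2.2414), the pooled rate is 0.265, the pooled standard error is √(2 × 0.265 × 0.735/24) = 0.1274 and the unpooled standard error is √((0.07 × 0.93 + 0.46 × 0.54)/24) = 0.1143. Power is Φ((0.39 − 2.2414 × 0.1274)/0.1143) = 0.820. The same formula gives 0.875 for the assumed 46% against 5%, so 82% is conservative there. The 95% normal half-widths are 1.96 × √(0.46 × 0.54/24) = 19.9 points, which matches the stated 20, and 1.96 × √(0.05 × 0.95/24) = 8.7 points, where the plan gives 8.

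**The case against.** The strongest defence is that the figure is right but lacks a qualifier. The chance that at least one of the two doses clears 10% is 0.9991. That event has a role in the plan, because protocol 10.3.3 allows the between-dose comparisons only if at least one arm clears the threshold. The sentence in 10.1 also names the two arms together without saying that it means each one. This may well be where the number came from. But the sentence does not say so. The rule is defined in each arm, the claim belongs to the individual dose, and the 82% given next in 10.1 is a per-comparison figure. A reader would take 0.999 as the chance for each dose, or for both, and it is wrong for either. What stands is that 0.9991 may be worth keeping under its own label.

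A second objection is that 0.97 does not describe the analysis now planned either. Protocol 10.6.1.1 asks for an interval suited to the stratified design. SAP 4.1.1 and 4.4.1 use all treated subjects and count those without a readable post-baseline biopsy as non-responders. This is fair as a caveat. As an illustration, suppose 15% of 28 subjects per arm became non-responders in this way and the rest kept a 46% rate. The effective rate would be 0.85 × 0.46 = 0.391, and P(X ≥ 8 of 28) would be 0.91, against 0.981 with no such loss. That moves the answer further from 0.999, and the sentence in 10.1 expressly names the exact interval.

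A third is weight: 24 per arm rests first on precision, and 0.97 is ample. This stands. It limits the consequence but does not make the figure correct.

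**Conclusion.** The concern holds. Under the rule that protocol 10.1 names, the probability is 0.971 per dose and 0.942 for both doses, not above 0.999. The chance that a given dose misses is 2.9%, roughly 30 times the stated ceiling of 0.1%. The chance that at least one of the two misses is 5.8%.

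These results rest on an unstratified exact interval, 24 analysed subjects per arm, a true rate of 46% in both arms and, for the joint figures, independent arms. If the 3 mg/kg rate is above 46%, which the protocol allows, that arm's probability is higher; it would reach 0.999 only at a rate of about 58%.

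This is an error in a reported design figure. It does not weaken the sample size, the threshold or the analysis.

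**What to change.** In protocol 10.1, replace the stated probability with about 0.97 per dose arm, corresponding to 7 or more responders of 24. If the at-least-one-dose figure was intended, add it separately and label it as such. If the protocol is closed, put the correction in the SAP or the study report. Say there that it refers to the exact interval with 24 subjects per arm and not to the all-treated analysis.

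Two optional clarifications can go in with the same edit. First, give the level and method behind the precision figures: the one introduced by "A sample size of 24 subjects will ensure an absolute precision of +/- 8" percentage points comes out nearer 9 by the formula that reproduces the 20. Second, say that the sentence promising that the sample "will ensure a power of 82% to detect a difference of 39% between two treatment arms" refers to 46% against 7%, and so is conservative for 46% against 5%.

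The cost is one number and a few words. No subjects are added, and no threshold, interval or analysis changes.
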